*We will work closely with the staff of another research study being conducted at the VA that has similar eligibility criteria, resulting in dual-eligible patients. In order to avoid patients being enrolled in both studies, which could result in patient burden, both studies will work with a statistician to identify these dual-eligible patients and randomly assign them to one study only prior to patient outreach and recruitment. 75% of these dual-eligible patients will be allocated to our study and 25% will be allocated to the other study in accordance with both programs' statistical power needs. Since both studies are similar in scope (e.g., weight loss, increasing exercise), we do not anticipate patients enrolled in one study will receive greater health benefits than patients enrolled in the other study.

Gender of Subjects

Subjects of both genders are included in the study.

Age of Subjects

The minimum age of the subjects is 18 and the maximum age is 75.

Racial and Ethnic Origin

There are no enrollment restrictions based upon race or ethnic origin.

Inclusion Criteria

Inclusion criterion: Having at least one HbA1c result in the prediabetic range (5.7-6.5%) in the 2 years prior to the start date of the study wave. In order to communicate with CHWs, patients must also speak either English or Spanish.

Exclusion Criteria

A diagnosis of DM, based on ICD-9 and ICD-10 codes applied during ambulatory encounters in the 2 years prior to the study wave; treatment with DM medication other than metformin (e.g. insulin or oral agents); age greater than 75 years; or exclusion by patient's PCP due to contraindication for lifestyle intervention or CHW outreach.

Vulnerable Subjects

The protocol includes collecting data from BH and VA clinical providers whose participation is vital to the success of the study. There is no coercion to enroll these clinic staff subjects. All such subjects can opt out by notifying the study staff that they would no longer like to participate in the study. Alternatively, subjects can decide not to complete surveys.

As we will be surveying a large random sample of pre-diabetic patients, it is possible that some of the survey respondents will be pregnant, mentally disabled, economically or educationally disadvantaged. Their exclusion from possible participation would prevent us from accurately sampling the population at random.

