CHW Recruitment: We will hire and train 6 CHWs (3@VA, 3@BH), from local patient support organizations (Veteran Service Organizations and BH volunteer office, as we have done in prior CHW studies) to implement the toolkit strategies. CHW employment opportunities announcements will be created. Requirements will include: 1) evidence of a leadership role in the patient community through social support or advocacy organizations; 2) strong communication and interpersonal skills; and 3) a high school education or GED. CHW candidates will not be required to have a background in health. Personal experience with DM will not be required.

CHW Training: We will train the CHWs in key DM concepts, motivational interviewing, brief action planning, and stages of behavior change. CHWs will participate in a 105-hour core competency training developed collaboratively developed by [name] and her team and the Community Health Worker Network of New York. CHWs will conduct mock telephone counseling calls with trained standardized patients to enhance skills, gain feedback, and develop confidence in these techniques. In addition to these training experiences, CHWs will have letter templates, motivational interviewing scripts, and protocols available for patient outreach to standardize and guide patient outreach

CHW Intervention

At each wave's outset, ~ 250 patients at each study site will be randomly selected for outreach and paired with one of five CHWs (2 at BH, 2 at VA, 1 at both clinics). Researchers will provide each intervention group PC provider their selected list of prediabetic patients. PCPs will be asked to review the list to identify anyone they think should be excluded from the intervention. Patients are matched to a CHW according to the patient's language and neighborhood of residence, as the study aims to cluster CHWs' patients to facilitate CHW travel and expertise in local resources. We mail selected patients a letter on behalf of their PCP alerting them of their DM risk status, available prevention resources, and introducing them to their assigned CHW. CHWs will then call patients to describe the program and seek verbal informed consent to enroll in the study. Patients who decline participation will be asked if they are willing to be invited again in subsequent waves of the study. CHWs will continue outreach until they have met their caseload for the wave.

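### Entry rules let a patient with an uncoded HbA1c above the entry range into the trial, where existing DM can be counted as an incident event and dilute the hazard ratio

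*Combined protocol and SAP*

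**What the plan says.** Inclusion Criteria: entry rests on "Having at least one HbA1c result in the prediabetic range (5.7-6.5%) in the 2 years prior" to the wave start. Nothing requires the latest or the highest value to lie in that range.

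Exclusion Criteria: existing diabetes is removed by "A diagnosis of DM, based on ICD-9 and ICD-10 codes applied during ambulatory encounters in the 2 years prior to the study wave", or by "treatment with DM medication other than metformin". No exclusion uses an HbA1c value. The same list includes "exclusion by patient's PCP due to contraindication for lifestyle intervention or CHW outreach".

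CHW Intervention: "Researchers will provide each intervention group PC provider their selected list of prediabetic patients", and "PCPs will be asked to review the list to identify anyone they think should be excluded from the intervention". The consent section adds that teams approve in advance the lists of patients who receive the intervention. No such review is described for controls, who are drawn at random from the control providers' patients (Number of Subjects; Statistical Power and Sample Size).

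Outcome: Control Group says that A1C results from routine care are needed for the main outcome. No section gives an HbA1c threshold, a confirmation rule or a baseline DM-free check for incident DM. Data Collection promises registry updates and data validation in general terms only.

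**The concern.** Take a patient with an in-range result 20 months before the wave and a result above the range last month, not yet coded, who is untreated or on metformin alone. This patient meets the inclusion criterion and no exclusion. PCPs in both arms are reminded to order follow-up A1C tests, so the condition is likely to be found soon after entry, and nothing in the plan stops it being recorded as incident.

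Applying the same rule in both arms prevents bias under the null, but it does not prevent dilution. Events that were already present at entry occur equally in both arms and pull the HR towards 1. The primary comparison covers only 12 months, when true events are few, so a small share of such patients matters.

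A second issue follows from the list review, which is described for intervention providers only. If that review took some of these patients out of the intervention arm's analysis, the remaining excess in the control arm would look like a benefit.

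**Working it through.** **Inputs from the plan.** 3-year DM incidence is 15% and there are 1,008 patients per arm (Statistical Power and Sample Size). The primary comparison is at 12 months (Data Analysis). The group size reproduces: 72 × 3.5 × 4 = 1,008. The 80% power cannot be reproduced, because no hazard ratio or difference is stated.

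**Assumed, because the plan gives no figure.** f is the share of selected patients with uncoded existing DM, taken as 1-3%, all becoming events within 12 months. r is the share of these removed by PCP review in the intervention arm, taken as 0, 10, 50 and 100%. The hazard is constant.

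**Step 1: 12-month incidence.** Annual hazard = -ln(1 - 0.15)/3 = 0.0542. The 12-month risk is 1 - exp(-0.0542) = 5.3%. With a true HR of 0.70 it is 1 - exp(-0.0542 × 0.70) = 3.7% in the intervention arm.

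**Step 2: existing cases kept in both arms (r = 0).** Observed risk = f + (1 - f) × true risk. Apparent HR = ln(1 - observed intervention risk) / ln(1 - observed control risk). For f = 2%:
- control: 0.02 + 0.98 × 0.0527 = 0.0717
- intervention: 0.02 + 0.98 × 0.0372 = 0.0565
- apparent HR = ln(0.9435)/ln(0.9283) = 0.78

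| f | Control risk | Intervention risk | Apparent HR (true 0.70) |
|---|---|---|---|
| 1% | 6.2% | 4.7% | 0.75 |
| 2% | 7.2% | 5.6% | 0.78 |
| 3% | 8.1% | 6.6% | 0.81 |

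With a true HR of 1.00 and r = 0, the apparent HR stays at 1.00 whatever f is. Over 3 years of follow-up the dilution is smaller: a true 0.70 appears as 0.72, 0.73 and 0.75.

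**Step 3: removal from the intervention arm's analysis only, true HR 1.00.** In that arm f becomes f(1 - r)/(1 - f × r); the control arm is unchanged.

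| r | f = 1% | f = 2% | f = 3% |
|---|---|---|---|
| 10% | 0.98 | 0.97 | 0.96 |
| 50% | 0.92 | 0.86 | 0.82 |
| 100% | 0.84 | 0.73 | 0.64 |

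The 100% row is an upper bound. These are ratios of cumulative hazards at 12 months. A Cox estimate may differ somewhat if the existing cases surface early.

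**The case against.** The strongest objection concerns the list review. A reader might infer that it biases the trial in favour of the intervention, and might take 0.64 as a plausible size. The documents do not support that reading, for four reasons.

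- The stated ground for PCP exclusion is a contraindication to lifestyle change or to CHW outreach, not known DM. Removal of DM cases is inferred from the open wording of the review step.
- The review excludes patients from the intervention, and Vulnerable Subjects describes such an exclusion as receiving no letter or coaching. Neither says that the patient leaves the analysis, and Data Analysis promises intention-to-treat. If they stay in, this bias disappears. The point remains open because that set is not defined and the sample-size text counts enrolled intervention patients.
- The group is narrow. The PCP must recognise the diabetes yet have entered no ambulatory code in two years and prescribed no DM drug other than metformin.
- The direction is not fixed. Dilution and one-sided removal pull opposite ways: with a true HR of 0.70 and half of these patients removed, the apparent HR would be 0.67-0.63 for shares of 1-3%.

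It can also be said that the underlying gap is the missing definition of incident DM. That is partly right, and the two should be repaired together. But a definition based only on post-entry results would still count a patient who was above the range before entry, so the baseline screen is needed as well.

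What stands untouched is the eligibility gap and the dilution, which need no assumption about what PCPs do.

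**Conclusion.** The eligibility gap is plain in the text and no other section closes it. Its main consequence is dilution: a true HR of 0.70 would appear as about 0.75-0.81 if 1-3% of patients enter with uncoded existing DM and all become events within 12 months. That share is an assumption. The documents do not show how many such patients there are, so it should not be read as established that the cohort contains them in these numbers.

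The one-sided review is a secondary, conditional point. It biases the HR only if PCPs remove some of these patients and the patients also leave the analysis set. Under no effect, the HR would then appear as 0.98-0.96 with 10% removed, 0.92-0.82 with 50%, and 0.84-0.64 at the upper bound of 100%, for shares of 1-3%. Share and removal rate are both assumed.

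**What to change.** 1. Before selection, and by one EMR query applied identically in both arms, exclude anyone with any HbA1c above the entry range in the 2-year look-back. Do not require the latest value to be in range: that would also drop patients whose value has fallen below 5.7%, who are not the problem.
2. Define any HbA1c-based event as a post-entry result above the entry range, so that one result cannot satisfy both entry and event.
3. For waves already enrolled, apply the same restriction to the analysis set in both arms, using pre-wave values only.
4. State that patients whom a PCP removes from outreach stay in the intention-to-treat set. This means defining that set from selection rather than from enrolment. It also guards against cases that the query misses.

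Cost: one more condition in the registry query, on data already held, and a smaller eligible pool. The pool matters most at the VA, where the plan counts about 1,100 eligible patients. Planned use there is 1,050 outreach contacts plus, if controls split evenly by site, about 550 controls: 1,600 in all. The number excluded by the query should be counted at each site before the rule is adopted. Recorded events also fall slightly: at shares of 1-3%, about 10 to 30 of the control arm's 63 to 82 (1,008 × f, and 1,008 × the control risks above). Those events carry no information about prevention.

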- 4. Develop, implement and assess strategies to recruit, train, and integrate peer CHW health coaches within the PCMH model.

The 36-month intervention will be conducted using a staggered entry design across four, overlapping, 12-month waves to account for CHW caseload limits. This study will test a scalable model of peer health coaching to address the millions of patients at risk for DM, using low cost, culturally congruent personnel to promote prevention of DM in PCMH practice. If successful, our study team will work with VA's Central Office and NY City's Health and Hospital Corporation to translate the model for larger scale implementation.

Characteristics of the Research Population

Number of Subjects

All 12 PC teams at VA NY Harbor and all 4 PCMH teams at BH will be eligible to participate. In our VA PROVE study, 51/52 PCPs participated in the intervention, and we expect similar rates in this project. Eligible patients will be identified through the study's pre-DM registry, which will be based on the EMR and Corporate Data Warehouse (CDW) at each site. This methodology builds on our ongoing national, retrospective cohort study of predictors of DM among veterans with pre-DM back to 2008. Based on preliminary analysis of VA NYHHS data from 2010-2012, 62% of veterans enrolled in PC without DM, have had an HbA1c test in the previous two years.

In the intervention group, we anticipate contacting 2,100 randomly selected patients (1,050 at the VA* and 1,050 at BH) to ultimately enroll about 1,100 patients (550 at the VA and 550 at BH). This outreach sample reflects our assumption that 20% of patients will be unreachable and that 60% of those reached will enroll in the study. Another 1,100 patients attributed to control group providers will be randomly selected as the control group, in accordance with the waiver of HIPAA authorization. As detailed below, the control group will not participate in the CHW intervention. The total sample, including the intervention and control groups, will be about 2,200 patients. This amounts to approximately 265 patients (across intervention and control groups) per wave and per clinical site.

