Such vulnerable patient populations may be excluded from CHW outreach as instructed by primary care physicians. (i.e. patient will not receive a letter about services or CHW coaching intervention).

Methods & Procedures

Control Group

The control group will not have access to CHWs. They will experience usual care in their primary care clinics. PCPs in the control group will receive reminders from the study team to order A1C tests for their patients in their study, as this pragmatically collected data is necessary to evaluate the study's main outcome.

Intervention Group: (CHW Health Coaching Integrated into Team)

CHWs will provide the diabetes prevention intervention, described below, to a randomly selected subset of eligible patients per wave in the intervention teams at each hospital. CHWs and the researchers will provide regular updates to the primary care providers in the intervention group on these activities. As with PCPs in the control group, intervention group providers will receive reminders to order follow-up A1C tests for their patients enrolled in the study.

Choice of intervention strategies for each patient: We will have patients across the entire spectrum of motivation. Since we target the full population at risk, it will include highly motivated patients, highly resistant patients and a large group in between with varying degrees of motivation and activation. Our toolkit driven approach, which includes a wide range of strategies aligned with patient activation levels, will be based on the same framework used when [name] helped revise the VA-DOD smoking cessation guidelines from a referral-based approach to a population-based one. In the revised guidelines, the underlying principle guiding all treatment decisions – which applies equally well in this proposed study – was *all patients should be offered treatment in the most intensive setting they are willing to attend*. Similarly, all patients with pre-DM will be encouraged to use the most intensive DM prevention intervention that they are willing to attend.

CHW Reach: We anticipate that up to 40% of pre-DM subjects will participate in hospital-based programs (MOVE! at VA and Healthy Lifestyles at BH) and another 10-20% will participate in the community based Diabetes Prevention Program (e.g. at local YMCAs).

Community Health Worker (CHW) Coaches - Recruitment and Training

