- *Maintenance*: After 6 months of intensive coaching, CHWs will transition to making monthly phone check-ins with patients for another 6 months to reinforce the knowledge and behaviors taught earlier.

Data Collection

Patient Data

As a pragmatic, population-based trial, we aim to understand the impact of our interventions on panels of patients in a real clinic environment and therefore will not collect any clinical data directly from patients. Instead we will rely on measurements taken during regular clinic visits and recorded in the EMR. We will access this clinical and administrative data for VA patients through the VA Informatics and Computing Infrastructure (VINCI), a secure, high performance interface with VA's Corporate Data Warehouse (CDW), and for BH patients from the NYC Health and Hospitals CDW. Relying on routinely collected clinical data does have its challenges. Patients in our cohort at baseline may not return to the clinic at appropriate intervals, and there may be incorrect information within the EMR limiting our ability to assess the impact of the interventions on all patients. Learning from our previous work, we will mitigate these challenges by updating the study registry regularly, and validating our data during Phase I of the study as we construct the pre-DM registries.

We will have the CHWs administer a survey (in person or by phone) of all intervention patients to assess patient activation and self-reported behaviors (diet and exercise habits). We will survey each wave's cohort of intervention patients twice: at baseline and at the end of their 1-year intervention phase. Surveys will include an MTA MetroCard worth \$11 to incentivize response. Non-responders will be mailed up to two reminders. A statement will be included with the survey outlining the number of times the survey will be conducted (two), the timeframe for the surveys (now, and one year from now).

Implementation Research

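### The diabetes exclusion looks back only 2 years at ambulatory codes, so patients with an older or inpatient-only diagnosis can enter and may be counted as incident

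*Combined protocol and SAP*

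**What the plan says.** All references are to the combined protocol and SAP.

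- **Entry.** Inclusion Criteria require "Having at least one HbA1c result in the prediabetic range (5.7-6.5%) in the 2 years prior to the start date of the study wave". One value in range is enough.
- **Exclusion by diagnosis.** "A diagnosis of DM, based on ICD-9 and ICD-10 codes applied during ambulatory encounters in the 2 years prior to the study wave". Older codes, inpatient codes and problem lists are not mentioned.
- **Exclusion by drug.** "treatment with DM medication other than metformin (e.g. insulin or oral agents". Metformin alone does not exclude.
- **Exclusion by the PCP.** The stated ground is "exclusion by patient's PCP due to contraindication for lifestyle intervention or CHW outreach"; earlier DM is not named. The CHW Intervention section describes the list review for one arm: "Researchers will provide each intervention group PC provider their selected list of prediabetic patients".
- **Outcome.** Statistical Power and Sample Size names the yearly hazard of incident DM as the primary outcome for power. The analysis section compares time to DM at 12 months. Neither gives a case definition. The Control Group section says of HbA1c results that "this pragmatically collected data is necessary to evaluate the study's main outcome".
- **Data quality.** The Patient Data section accepts that "there may be incorrect information within the EMR limiting our ability to assess the impact of the interventions on all patients", and plans registry updates and a Phase I validation. It specifies no check for prevalent DM.
- **Sizing.** The sample-size section removes diagnosed DM (25% at the VA, 15% at BH) without repeating the 2-year or ambulatory limit.

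**The concern.** A diagnosis already on record before the wave starts is not a new case, whatever the latest HbA1c shows. The stated look-back discards part of that record. Someone coded 3 or more years ago, or only during an admission, who is diet-controlled or on metformin and has one value in range, passes every rule.

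Nothing later in the plan takes such a patient out of the at-risk set. Any event counted for them is one that coaching could not have prevented, and it falls in an endpoint with few events. Spread equally over the arms, these events pull the hazard ratio towards 1 and cost power. Spread unequally, they bias it.

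**Working it through.** **1. The plan's own figures.** Enrolment reproduces: 72 × 3.5 × 4 = 1,008, and 2,100 × 0.8 × 0.6 = 1,008. The stated 80% power cannot be reproduced, because no hazard ratio or detectable difference is given.

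**2. Expected events.** The plan assumes 15% DM incidence over 3 years. At constant hazard the 12-month risk is 1 − 0.85^(1/3) = 5.27%. In 1,008 controls that is 1,008 × 0.0527 = about 53 events.

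**3. Dilution (assumed inputs).** The documents give neither the share of entrants with earlier DM nor the proportion who would be counted. Assume shares of 1-3%, with 30-60% counted within 12 months. Spurious events per 100 are s = share × proportion counted, so s runs from 0.01 × 0.30 = 0.3 to 0.03 × 0.60 = 1.8 per 100. Adding s to both arms with a true HR of 0.70:

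observed HR ≈ (0.70 × 5.27 + s) / (5.27 + s)

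| Share | Counted | s per 100 | Observed HR | Spurious share of control events |
|---|---|---|---|---|
| 1% | 30% | 0.3 | 3.989/5.57 = 0.72 | 5% |
| 1% | 60% | 0.6 | 4.289/5.87 = 0.73 | 10% |
| 3% | 30% | 0.9 | 4.589/6.17 = 0.74 | 15% |
| 3% | 60% | 1.8 | 5.489/7.07 = 0.78 | 25% |

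**4. Are the inputs compatible?** To enter, a patient with older DM must have had no ambulatory DM code for 2 years. If the yearly coding probability is constant at 60%, only 0.4² = 16% escape. A 3% share then needs a stock of older DM equal to 0.03/0.16 = about 19% of the cohort's size. At 30% a year, 0.7² = 49% escape, and a 1% share needs 0.01/0.49 = about 2%. A high share and frequent re-coding work against each other, so the last row is the least likely.

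**5. Power.** With 1,008 per arm, two-sided 0.05 and no clustering, power = Φ(√events × |ln HR| / 2 − 1.96). At 12 months, 80% power needs HR 0.539 (about 82 events, intervention risk 2.88%). Let a share f be prevalent and half of them be counted, so that each arm's risk is (1 − f) × true risk + 0.5f:

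- f = 1%: control 0.99 × 5.27% + 0.5% = 5.72%; intervention 0.99 × 2.88% + 0.5% = 3.35%. HR = ln(1 − 0.0335)/ln(1 − 0.0572) = 0.58; power about 75%.
- f = 2%: HR 0.61, power about 69%.
- On the 3-year 15% basis (HR 0.707 needed, about 260 events), power falls only to about 78% and 76%.

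**6. Direction.** Two features could make the effect unequal. Both sums below assume no true effect.

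- CHWs contact intervention patients when visits are due. If that raised the proportion counted from 30% to 60% in that arm only, a 1% share gives (5.27 + 0.6)/(5.27 + 0.3) = 1.05, against the intervention.
- PCP list review is described for intervention providers only. If it removed half the prevalent cases there, with half of the rest counted, f = 1% gives control 5.72% and intervention 0.995 × 5.27% + 0.25% = 5.50%, an HR of 0.96. At f = 3% it is 0.90. Both favour the intervention.

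**The case against.** A reader might infer that these patients will be counted as incident at their next DM code. The documents do not support that. Incident DM is undefined, and the one pointer, in the Control Group section, is to HbA1c. Under an HbA1c-only definition a new code creates no event. A prevalent patient could still count at the next raised value, but at a different and unknown rate. What stands is that they may be counted.

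A reader might also infer a clear one-sided bias from visit prompting. HbA1c reminders go to PCPs in both arms, and control teams receive reports of patients due for testing. CHW contact still differs by arm, but one-arm list review could act in the opposite direction.

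Other counter-arguments:

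- **Size.** The illustrative inputs have no source. At the low end, 0.70 becomes 0.72, which is small. Both points stand.
- **Validation.** Phase I validation and PCP review might catch some cases. Neither is specified to look for earlier DM.
- **Metformin.** The CHW Intervention section lists it as a prevention option, so its use does not mark prevalent DM and its eligibility is deliberate. This stands.
- **Feasibility.** Number of Subjects says the registry method builds on a "national, retrospective cohort study of predictors of DM among veterans with pre-DM back to 2008". That covers veterans only. For BH, the sample-size section mentions 5 years of HbA1c results, not older diagnosis codes. This stands as a limit on the fix.

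**Conclusion.** The entry gap is explicit and should be closed. The exclusion admits patients whose earlier DM is already on record, and neither a case definition nor an at-risk rule keeps them out of the primary endpoint.

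The size is unknown. Under the assumed inputs, a true HR of 0.70 would read about 0.72-0.78, with values near 0.78 unlikely. These figures rest on constant hazard, equal contamination of the arms and no clustering; they show sensitivity and are not estimates. The 12-month comparison is more exposed than a 3-year one, because only about 53 control events are expected. The net direction cannot be settled from the documents.

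**What to change.** 1. Before selection in each remaining wave, run one identical query in both arms over all available VA and BH history and all encounter types. Exclude patients with an earlier DM diagnosis, preferably by a confirmed-code rule so that a single miscoded visit does not exclude.
2. For waves already enrolled, flag these patients in both arms using only records dated before wave start. Remove them from the DM at-risk set and report the result with and without them. The counts will also supply the missing share.
3. State the incident-DM definition that this at-risk set serves: data sources, criteria and any confirmation rule.

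Metformin eligibility need not change.

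**Cost.** A longer query and a slightly smaller pool. The loss matters most at the VA, where about 1,100 are eligible and 1,050 are to be contacted for the intervention arm alone. The depth of BH diagnosis history must be confirmed first. If it is short, the look-back achieved at each site should be reported. No new patient contact is needed.
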